#### 4.4. Study groups, randomisation, and stratification

Asymptomatic men and women aged 50 to 69 years from each participating Autonomous Region will be identified through the corresponding Community Health Registry (CHR) for enrolment into this study. Randomisation will be carried out prior to invitation, with computer-generated lists in blocks of 4 (block randomisation) from the list of health cards, after having previously grouped individuals by household (specified by street address, floor, and apartment number) (see Processes of selecting and inviting the population to be screened section).

All eligible patients will be randomised (1:1 ratio) to the two study groups:

Group 1: Screening by biennial FIT (latex agglutination, OC-Sensor®, cut-off point: 75 ng Hb/ml, corresponding to 15 µg Hb/g of feces), and colonoscopy (after no more than 1 month) for patients with a positive result. Determination of FIT will be made using a single faecal sample, without dietary restriction or interruption of normal treatment of the individual, although the habitual use (>1 month) or recent use (last 7-15 days) of NSAIDs, aspirin, anti-platelet drugs and anticoagulants will be recorded. The above-mentioned cut-off point was used in the baseline round; in subsequent rounds, we decided to modify the cut-off to 20 µg Hb/g of feces since it is the one accepted in the Spanish population-based CRC screening program.

Group 2: Screening by one-time colonoscopy. The ongoing use (>1 month) or recent use (last 7-15 days) of NSAIDs, aspirin, anti-platelet drugs and anticoagulants will also be recorded.

Individuals in Group 1 or Group 2 who do not agree to the type of testing assigned to them may require receiving the alternative test and must still be followed up in order to carry out efficacy analysis according to the intention to screen analysis. The choice of the alternate test will not be actively offered to individuals invited to the study and, accordingly, COLONPREV is not considered a study of sequential screening test offers.

Information on the long-term status of individuals in Group 1 or Group 2 who do not agree to participate in the study will be obtained through population-based registries at the completion of the trial in order to assess efficacy according to the intention to screen analysis.

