## 7. STATISTICAL ANALYSIS PLAN (SAP)

Because of the study design, which allows for cross-over between both strategies, the main outcomes of the study will be analysed by intention-to-screen, as-screened and per-protocol.

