### As-screened

Cumulative incidence curves for the screening procedure actually performed will be estimated with the Kaplan-Meier estimator, considering the period from the day of randomization to the end of follow-up. The Kaplan-Meier estimator with daily outcome events will be used to compute the probability (risk) of the outcome during the period. For CRC incidence and mortality, non-CRC events will be considered as censoring events. We will calculate the 10-year risk differences and risk ratios between the trial arms, and 95% CI will be computed using the normal approximation. To provide adjusted estimates, the Kaplan-Meier estimator will be weighted with inverse probability of weighting (IPW). In this causal contrast, propensity scores for colonoscopy, FIT and no screening will be estimated with a multinomial logistic regression. The included covariates will be age, sex and centre of participants with a 3-degree of freedom natural spline.

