### Per-protocol

Cumulative incidence curves for the compliers (i.e. those individuals who completed the treatment originally allocated) will be estimated with the Kaplan-Meier estimator, considering the period from the day of randomization to the end of follow-up. The Kaplan-Meier estimator with daily outcome events will be used to compute the probability (risk) of the outcome during the period. For CRC incidence and mortality, non-CRC events will be considered as censoring events. We will calculate the 10-year risk differences and risk ratios between the trial arms, and 95% CI will be computed using the normal approximation. To provide adjusted estimates, the Kaplan-Meier estimator will be weighted with IPW. In this causal contrast, propensity scores for colonoscopy, FIT and no screening will be estimated with a multinomial logistic regression. The included covariates will be age, sex and centre of participants with a 3-degree of freedom natural spline.

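### As written, the per-protocol weights ignore randomised arm, so compliers' relative weights are wrong wherever the ratio of cross-over to adherence varies with age, sex or centre

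*Combined protocol and SAP*

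**What the plan says.** Section 7 plans three analyses of the main outcomes and gives cross-over as the reason: "Because of the study design, which allows for cross-over between both strategies". Section 4.4 lets people in either group who decline their assigned test ask for the other one; they "may require receiving the alternative test".

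The as-screened analysis groups people by what they had: "Cumulative incidence curves for the screening procedure actually performed". The per-protocol analysis is confined to "compliers (i.e. those individuals who completed the treatment originally allocated") and reports 10-year risk differences and risk ratios between the trial arms.

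The weighting text is the same, word for word, in both subsections. In the Per-protocol subsection, "the Kaplan-Meier estimator will be weighted with IPW", "propensity scores for colonoscopy, FIT and no screening will be estimated with a multinomial logistic regression", and "The included covariates will be age, sex and centre of participants with a 3-degree of freedom natural spline". Neither subsection lists randomised arm as a covariate or says that the model is fitted separately by arm.

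**The concern.** The model matches the as-screened analysis, where group membership depends only on the procedure received. Per-protocol membership depends on procedure and arm together: a person counts only if the procedure received is the one allocated. The probability to invert is then that of taking the allocated test given arm and covariates. A model without arm returns the probability of having the procedure from either arm, which mixes compliers in one arm with cross-overs from the other.

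Where cross-over into a test is large relative to adherence, compliers with those covariates get too little weight, and other compliers get relatively too much. Weighting that is meant to restore each arm's covariate mix can then distort it. What is at stake is the adjusted per-protocol risk difference and, mainly, the risk ratio for CRC death and CRC incidence.

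**Working it through.** The plan gives no figure to reproduce here. The check is algebra followed by worked examples.

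**Inputs from the documents**
- Allocation is 1:1 (section 4.4), so the probability of each arm is 0.5 at every covariate level.
- Overall compliance is expected to be 30% (section 4.5). Most examples below use it as adherence to the assigned test.
- The non-inferiority margin is 1.6% absolute, or 160 per 10,000 (section 4.5).
- No cross-over rate is given, overall or by age, sex or centre. All cross-over patterns and risks below are assumptions, and receipt of the test is treated as a single event.

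**Algebra.** Let L be age, sex and centre; c(L) adherence to the allocated test; x(L) the proportion of the other arm who cross over into that test.
- Needed weight: 1/c(L).
- Weight from a model without arm: 1/[0.5c(L) + 0.5x(L)].
- Planned over needed: 2c/(c + x) = 2/(1 + x/c).

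A constant factor cancels in a weighted Kaplan-Meier estimate. Relative weights are therefore right only if x/c is constant over L.

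**Example 1: FIT arm alone.** Assume equal numbers aged 50-59 and 60-69, with 10-year risks of 0.2% and 0.5%. The correct arm risk is 0.350%. The weighted share of each age group is proportional to 1/(1 + x/c).

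| x/c younger / older | Older share | FIT risk | Relative error | Absolute error per 10,000 |
|---|---|---|---|---|
| 0.10 / 0.20 | 0.8333/(0.9091 + 0.8333) = 0.478 | 0.3435% | -1.9% | -0.65 |
| 0.10 / 0.30 | 0.7692/(0.9091 + 0.7692) = 0.458 | 0.3375% | -3.6% | -1.25 |
| 0.05 / 0.50 | 0.6667/(0.9524 + 0.6667) = 0.412 | 0.3235% | -7.6% | -2.65 |

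The relative error passes unchanged to the risk ratio if the colonoscopy weights are right.

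**Example 2: both arms, no true difference.** Assume two equal age groups with risks of 0.1% and 0.4%, so the correct older share is 0.500 and the correct risk is 25 per 10,000. Pairs are younger/older. RD is FIT minus colonoscopy, per 10,000.
- No cross-over, adherence 35%/25%: weights correct.
- Cross-over exactly proportional to adherence: weights correct.
- Constant 5% cross-over, adherence 35%/25%: factors 0.70/0.40 = 1.750 and 0.50/0.30 = 1.667. The older share is 0.488 in both arms; weights are wrong but RD is 0.
- Cross-over 10%/5% into both tests, adherence 30%: older share 0.533 in both arms, RD 0.
- Cross-over into FIT 10%/4%, into colonoscopy 1%/1%, adherence 30%: FIT factors 0.60/0.40 = 1.50 and 0.60/0.34 = 1.76; older share 0.541; FIT risk 10 + 30 × 0.541 = 26.2 against 25.0. RD +1.2, risk ratio 1.05.
- Cross-over into FIT 15%/5%, into colonoscopy 2%/1%, adherence 30%: older share 0.562 (FIT) and 0.508 (colonoscopy). RD +1.6, risk ratio 1.07.
- The same pattern reversed by age: RD -1.6, risk ratio 0.93.

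**Example 3: simulation of 400,000 people, no true difference.** Adherence is 30%, cross-over from colonoscopy to FIT falls from 15% at age 50 to 5% at age 70, cross-over from FIT to colonoscopy is 1%, and risk rises with age.
- Multinomial model without arm: weighted mean age 60.0 (colonoscopy) and 60.4 (FIT); RD +0.81; risk ratio 1.036.
- Arm added as a main effect: RD +0.73; risk ratio 1.032.
- Arm plus arm-by-age terms: RD -0.04; risk ratio 0.998.

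**The case against.** The strongest reply is that the plan does not say on whom the model is fitted. Each arm can contain all three outcomes, so a multinomial model fitted within each arm would also have these three levels and would give the right probability. That stands as far as it goes: a fit within arm is not excluded, and one sentence would settle the matter. But the covariate list is explicit and omits arm, and the text is identical to that of the as-screened analysis. The literal reading is one pooled model.

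The second reply is size. The alternative test is not actively offered (section 4.4), so cross-over may be rare. With FIT uptake of 30%, the extreme row of Example 1 needs 0.50 × 30% = 15% of older Group 2 invitees to take FIT at their own request, which is hard to credit. Even then, 2.65 per 10,000 is under 2% of the 160 per 10,000 margin. This stands too.

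A reader might infer that variation in cross-over alone drives the error, that colonoscopy compliers keep the right mix, or that FIT risk will be understated. None of these is supported. The ratio x/c is what matters, cross-over is allowed in both directions, and the reversed pattern changes the sign.

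**Conclusion.** The point holds on the literal text. The planned per-protocol weights give the wrong covariate mix whenever cross-over relative to adherence varies with age, sex or centre. Bias in the arm contrast needs two further conditions: the covariate predicts the outcome, and the error differs between arms.

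The actual size cannot be known from the documents. It is nil without cross-over. Under the assumed patterns the risk ratio is off by a few percent, at most about 7-8%, and the absolute risk by about 1 to 3 per 10,000.

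A reader might go further and infer that the non-inferiority conclusion is at risk. The documents do not support that. The margin and sample size are tied to the intention-to-screen analysis, which uses no such weights, and the absolute error is small against the margin. The as-screened analysis is also unaffected, because the pooled model fits its grouping. This is a modest defect in the adjusted per-protocol estimates, worth correcting because the correction is cheap.

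**What to change.** In the Per-protocol subsection of section 7, state that adherence is modelled separately within each randomised arm, and that each complier is weighted by 1/P(received allocated test | arm, age, sex, centre). A single model that includes arm and its interactions with age, sex and centre is an alternative. Arm as a main effect alone is not enough, as Example 3 shows. Keep the pooled multinomial model for the as-screened analysis only, and say so.

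The cost is a sentence or two in the SAP and a few lines of code, with no new data. The downside is a few more parameters and possibly sparse centre cells within an arm. Reporting cross-over by arm, age group, sex and centre would let readers judge how much the choice matters.

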### **End points of the study**

#### Primary end point:

*CRC-specific mortality at 10 years*

#### Secondary end points:

1. *Participation, detection rate, diagnostic yield and complication rate at the completion of the first round and at the end of study (10 years)*

Definitions of these four key outcomes are as follows:

- Participation: number of participating individuals (i.e. individuals who completed colonoscopy in the colonoscopy group and individuals who returned the test in the FIT arm) relative to the number of eligible individuals.
- Detection rate: number of true positives relative to the number of participating individuals.
- Diagnostic yield: number of true positives relative to the number of eligible individuals.
- Complication rate: number of major complications (i.e. perforation, postpolypectomy bleeding requiring hospitalization, and cardiovascular/pulmonary complications requiring medical management) relative to the number of participating individuals.

Differences in these four key outcomes between both strategies will be established by logistic regression analysis, adjusted by age, gender and participating centre, and reported as odds ratios (OR) with 95% CI.

*2. Overall survival at the end of study (10 years)*

*3. CRC incidence at the end of study (10 years and 15 years)*

*4. Cost-effectiveness analysis*

Cost-effectiveness will be studied with a Markov's model at the completion of study. Results will be reported in terms of quality-adjusted life years (QALY).

*5. Analysis of factors influencing participation in the study*

Factors associated with participation at the completion of first round and at the end of study (10 years) in each screening strategies will be analysed by logistic regression analysis and results reported as OR with 95% CI. Parameters analysed will include demographics, personal and familial characteristics, socio-economic status, etc.

*6. Number needed to screen to detect a colorectal cancer*

The number needed to screen to detect a CRC will be calculated using the inverse of risk (i.e. the number of participants receiving a given screening modality divided by the number of positive cases in that given modality), with 95% CI computed using the inverse of the binomial standard approximation.

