#### **3.2. Secondary objectives**

- To compare diagnostic yield and detection rate of CRC and/or advanced adenomas in each screening strategy at the completion of the first round.
- To compare the participation rate in each screening strategy at the completion of the first round, and identify the factors influencing it (i.e. demographics, personal and familial characteristics, socio-economic status, etc.).
- To compare overall diagnostic yield and detection rate of CRC and/or advanced adenomas in each screening strategy at 10 years.
- To compare the overall adherence rate in each screening strategy at 10 years, and identify the factors influencing it.
- To assess the cost-effectiveness of each screening strategy.
- To assess the rate of serious complications in each screening strategy, both at the completion of the first round and overall at 10 years.
- To compare CRC incidence in each screening strategy at 15 years.

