## 5. DEVELOPMENT OF THE STUDY

This research project is included within the population-based screening programme of each Autonomous Region. This screening programme will ensure the recall of individuals for appointments in successive rounds of screening, while also continuing the strategy assigned to them during the randomisation of the study. The investigators will also be responsible to electronically or manually transfer to the LSO the information derived from the study that is of interest to the population screening programme.

Each Autonomous Region is committed with recruiting the same number of individuals regardless of the number of participating health centres or hospitals in each region.

The dynamics of the study are summarised as follow:

- Participants in Group 1 with a negative FIT will remain in their assigned group and will be offered the next round of screening at 2-year intervals until the age of 69. All of them will be sent a letter informing them of the test result and the date of the next round of screening. Individuals who enter the study at the age of 68 or 69 will undergo a single round of screening.
- Participants in Group 1 with a positive FIT will be contacted by phone and sent a letter informing them of the test result and the date of their appointment with the primary care physician (or specialist) or the person responsible for the screening programme, depending on the Autonomous Region. They may be assisted in this task by the project staff. During the visit they will be informed about the colonoscopy procedure and will be scheduled for this procedure.
- Participants in Group 1 with a positive FIT but who have normal colonoscopies or in whom only non-neoplastic disease is detected will remain in the FIT arm and will be offered the next round of screening using the biennial FOBT test at 10 years after performance of the colonoscopy.
- Participants in Group 2 who are found to be negative in colonoscopy or in whom only non-neoplastic disease is detected, will remain in the colonoscopy arm and will be offered a new colonoscopy at 10 years after performance of the baseline colonoscopy.

Surveillance colonoscopy for patients with adenomas will be carried out according to the Joint Guideline from the *US Multi-Society Task Force (USMTF)* (45).

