### Phase 2 (individuals who require retesting):

- In Group 1, it begins with repetition of the FIT test in patients for whom the previous test was invalid and ends when it is delivered and properly read.
- In Group 2, it begins with repetition of colonoscopy in cases in which the bowel preparation was inadequate, or repetition of colonoscopy or performance of CT-colonography when the colonoscopy was incomplete.

Phase 3: includes all Group 1 respondents for phases I and II who are included in the subsequent biennial rounds until completion of the 10 years. In Group 2, phase III will be completed 10 years after completion of the first examination.

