## 6. DEFINITIONS

- *Pragmatic study*: study designed to clarify whether an intervention works under real-life conditions and whether it works in terms that matter to the patient. It is simply concerned with whether the intervention works, not how or why.
- *Target population*: 50-69 year-old individuals with verified address in sanitary card.
- *Invited population*: target population excluding non-contacted individuals.
- *Eligible population*: target population excluding non-contacted and excluded individuals.
- *Participant population*: individuals who returned the FIT test (Group 1) or who completed colonoscopy (Group 2).
- *Screening inclusion data*: data of sending the invitation letter.
- *Incomplete colonoscopy*: colonoscopy in which caecal intubation is not possible. When an incomplete colonoscopy occurs, this examination must be repeated or completed with a CT-colonography.
- *Inadequate colon cleansing*: when less than 90% of colorectal mucosa can be properly evaluated due to the presence of faeces, this examination must be repeated.
- *Non-neoplastic polyp*: hyperplastic, hamartomatous or inflammatory polyps.
- *Non-advanced adenoma*: any tubular adenoma <1 cm and with low-grade dysplasia.
- *Advanced adenoma*: adenoma >1 cm in size, or with high-grade dysplasia, or with villous component (>25%).
- *High-risk adenoma*: 3 or more non-advanced adenomas, or any advanced adenoma.
- *Low-risk adenoma*: 1 or 2 non-advanced adenomas.
- *Non-invasive colorectal cancer*: colorectal carcinoma without submucose invasion (pTis). It includes intramucous carcinoma and intraepithelial carcinoma.
- *Invasive colorectal cancer*: colorectal carcinoma beyond the *muscularis mucosa* (pTNM stages I, II, III and IV).
- *Advanced neoplasia*: colorectal advanced adenoma or cancer.
- *Malignant polyp*: adenoma that harbours an area of carcinoma invading submucose (pT1).
- *Polyposis*: existence of >10 polyps. Depending on the histology, it could be adenomatous, hamartomatous or hyperplastic.
- *Non-neoplastic colorectal diseases*: any non-neoplastic disease detected in the colonoscopy (i.e. haemorrhoids, diverticulosis, angiodyplasia, etc.).

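### The SAP has no multi-round measure for the 10-year adherence objective, and its participation count, taken literally, cannot show drop-out from biennial FIT

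*Combined protocol and SAP*

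**What the plan says.** Section 3.2 separates two objectives. One concerns the participation rate at the first round. The other is "To compare the overall adherence rate in each screening strategy at 10 years, and identify the factors influencing it".

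Section 7 has no end point called adherence. Item 1 of the secondary end points covers participation and three other outcomes, to be reported both after the first round and at 10 years. Participation has a single definition for both times: "individuals who completed colonoscopy in the colonoscopy group and individuals who returned the test in the FIT arm", taken "relative to the number of eligible individuals". Section 6 defines the participant population in the same way. Item 5 analyses factors associated with participation at both times by logistic regression.

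The strategies differ in what they ask of people. Group 2 has one colonoscopy. Participants in Group 1 with a negative FIT "will be offered the next round of screening at 2-year intervals until the age of 69" (section 5). The number of rounds due therefore depends on age at entry: "Individuals who enter the study at the age of 68 or 69 will undergo a single round of screening". After a positive FIT, section 5 leads either to a 10-year gap before the next FIT or to colonoscopic surveillance, so biennial rounds stop.

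No section gives a minimum number of FIT rounds, a rate per round, a denominator of rounds due, or a rule for people who stop.

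**The concern.** A repeated test and a one-time examination differ most, operationally, in whether people keep coming back. The background in section 2 itself presents better compliance as a possible advantage of a ten-year colonoscopy interval. An end point that scores a person once, for returning a FIT, cannot test that.

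In Group 2 the count means the allocated strategy was completed. In Group 1 it can mean one round out of five. A 10-year odds ratio built on it would set full completion in one arm against any single return in the other. The item 5 regression uses the same yes/no outcome, so at 10 years it would describe who ever returned a test, not who stayed in the programme.

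**Working it through.** The documents state no 10-year adherence figure, so there is none to reproduce. The check has two parts.

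**Reading the definition at 10 years.** Numerator and denominator are both counts of persons. Two readings of who is invited later give different figures, and neither shows drop-out:

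- Of the third screening phase, section 5.1 says that it "includes all Group 1 respondents for phases I and II who are included in the subsequent biennial rounds until completion of the 10 years". If only earlier respondents continue, nobody new can enter the numerator, and the 10-year count equals the first-round count.
- Section 5 says later rounds use the same invitation system, according to each region's policy. If non-responders are re-invited, the count becomes ever returned and can only rise. As an extreme, independent uptake of 30% at each of five rounds gives 1 - 0.7^5 = 83.2% ever returning, but 0.3^5 = 0.24% returning all five.

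**Size, as an illustration.** Assumptions, none of them from the documents: entry ages uniform over the 20 ages 50-69; rounds at years 0, 2, 4, 6 and 8; a constant fraction r of those who returned one round return the next; no return after a miss; nobody leaves the schedule after a positive FIT. From section 5: rounds are offered up to age 69.

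Rounds due by entry age: 50-61, five (12 ages); 62-63, four; 64-65, three; 66-67, two; 68-69, one. The last entry agrees with the plan's own statement about entrants aged 68 or 69. The mean is (12×5 + 2×4 + 2×3 + 2×2 + 2×1)/20 = 80/20 = 4.0, and 8 of 20 ages are due fewer than five.

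Among first-round participants, the proportion returning all due rounds is 0.6r^4 + 0.1(r^3 + r^2 + r + 1):

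- r = 0.7: 0.6×0.2401 + 0.1×2.533 = 0.397
- r = 0.8: 0.6×0.4096 + 0.1×2.952 = 0.541
- r = 0.9: 0.6×0.6561 + 0.1×3.439 = 0.738

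For a person due k rounds, the expected share returned is S_k = (1 + r + ... + r^(k-1))/k. The mean share is 0.6×S_5 + 0.1×(S_4 + S_3 + S_2 + S_1):

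- r = 0.7: 0.6×0.5546 + 0.1×(0.6333 + 0.7300 + 0.8500 + 1) = 0.654
- r = 0.8: 0.6×0.6723 + 0.1×(0.7380 + 0.8133 + 0.9000 + 1) = 0.749
- r = 0.9: 0.6×0.8190 + 0.1×(0.8598 + 0.9033 + 0.9500 + 1) = 0.863

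In all three cases the person-level count retains 100% of first-round participants. On the scale of eligible individuals, take the 30% compliance in section 4.5 as first-round uptake (the section does not say what it refers to) and assume no late entrants. The count then stays at 30%, while the proportion returning all due rounds is 0.30×0.397 = 11.9%, 0.30×0.541 = 16.2% or 0.30×0.738 = 22.1%.

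**The case against.** The strongest reply is that the SAP never ties the adherence objective to the participation definition and never says that one FIT in ten years is enough. At 10 years, returning the test could mean ever, at the last round, or at each round due. This stands. A reader might infer that the plan deliberately equates one FIT with full adherence, and the documents do not support that. Strictly, 10-year adherence is undefined, and the concern describes what follows if the one stated rule is applied as a count of persons. The correction is the same either way.

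A reader might also infer that the 10-year figure must equal the first-round figure, so that the 10-year regression repeats the first-round one. That follows only from the restrictive reading of Phase 3; with regional re-invitation it does not.

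Another tempting step is to assume everyone is due five rounds. Completion of all rounds would then be r^4 = 24%, 41% or 66%, which overstates the loss because 40% of the assumed entry ages are due fewer. The age-specific figures above are the ones to use. They still ignore intermittent return and departures after a positive FIT.

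It may be said that the per-protocol analysis covers the point. Its compliers are those who completed what they were allocated, but the number of FIT rounds needed is not given, and the set serves the risk curves, not the adherence objective.

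Finally, drop-out is hidden in the end point, not necessarily in the data. Section 5.2 says test results go to the central database, though it does not mention invitations or rounds offered.

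**Conclusion.** The concern holds in this form: the 10-year adherence objective has no multi-round measure, and the only stated rule, applied literally, gives one FIT the same credit as all due rounds. Under the assumed 70-90% retention per round and uniform entry ages, that rule shows no loss among first-round participants, while 40-74% return all due rounds and the mean share of due rounds returned is 65-86%. The range depends on retention and age assumptions that the documents neither give nor contradict; the conclusion that the count cannot register drop-out does not depend on them.

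The scope is limited to a secondary objective and its factor analysis. CRC-specific mortality by intention to screen does not use the participation definition and is unaffected. The change is worth making, but it is not critical to the trial's main conclusion.

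**What to change.** Keep the present participation definition for the first round. For 10 years, add to section 7:

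- **Group 1 adherence:** FIT rounds returned divided by rounds due. Rounds cease to be due after age 69, a positive FIT, a colonoscopy (including by cross-over), entry to surveillance, CRC, death or emigration. State whether first-round non-responders remain due for later rounds.
- **Group 2 adherence:** one due examination, completed or not.
- **Cross-overs:** state how they count in each arm. Without this, a Group 1 person who chose colonoscopy could be scored as missing FITs.
- **Reporting:** alongside the share of due rounds, give the proportions returning all due rounds and at least one. Report completion of colonoscopy after a positive FIT separately, so that the participant definition in section 6 is kept.
- **Factor analysis at 10 years:** logistic regression on all due rounds completed (yes/no), or a grouped binomial model for rounds returned out of rounds due, with robust standard errors.

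The cost is SAP wording and some programming, plus linkage to regional invitation records if rounds offered are not held centrally. The reported FIT adherence figure will be lower than the person-level count if people drop out.
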